Four sessions as summarized below will be delivered by a trained community wellness coach. We will aim to conduct the first two sessions in person, and to offer subsequent sessions on a weekly basis by phone. The interventionist and participant will jointly determine the optimal timeframe for completing the four sessions within 12 weeks of enrollment.

| One-on-One Sessions | |
|---------------------|---|
| Session | Content |
| 1 | Challenges of asthma in children and families; the role of stress and introduction of tools for stress management; breathing exercise |
| 2 | Introduction to mindfulness; meditation |
| 3 | Positive thinking, self-nurturing and relaxation exercises |
| 4 | Working together with your child in deep breathing and mindfulness Wrap up: Encourage continuing utilizing peer support. |

Intervention Component 2: Peer Support

Participants will also be invited to participate in support groups conducted on a rolling basis, for up to six months after enrollment. The community wellness coaches will facilitate these sessions. A portion of each session will be devoted to content related to stress management and/or asthma management, to be provided by a clinician or community-based expert as appropriate, with the remainder of the time used for facilitated discussion and support. Topics will be announced in advance so that participants know what to expect and can bring questions if desired.

Content from the intervention sessions will be reinforced by periodic text messages and calls from the coaches, who will also encourage ongoing participation in the support groups.

Certificates will be provided to participants who complete core intervention activities to foster a sense of accomplishment and expertise.

Once control group participants have completed all study activities, they will be offered the opportunity to receive the intervention content.

D.4. Participants

We will consent a cohort of up to 400 parent-child dyads, with the goal of randomizing up to 250 dyads. Parents will be the primary targets of the intervention, and both parent and child outcomes will be assessed, as described in D.6. Outcomes.

Eligible parents will meet the following criteria:

- self-identify as African-American
- be both the legal guardian and primary asthma caregiver of an eligible child
- not have an exclusionary psychiatric condition, including but not limited to psychosis, based on the screening form at recruitment

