The community wellness coaches that implement the intervention will be selected based on prior experience promoting healthy lifestyle behaviors in community settings, including individuals with experience as a community health worker, a practitioner of complementary and integrative health therapies. They will be employed by Children's National, and will participate training activities and ongoing supervision with our research team staff. Training will be led by Drs. [name] and [name], and topics will include:

- human subjects research, privacy protections, and informed consent,
- socialization with other coaches,
- an overview of this study and the role of coaches,
- coach interaction guidelines (e.g., confidentiality, rapport building, active listening,

- crisis/emergency situations),
- role-playing mentorship skills, and
- an overview of participant assignment, call structure, and supervision

Emphasized throughout the training will be the supportive role of the coach, and the distinction between their role and that of a health care team provider. Coaches will be trained to *not* give any medical advice and to refer participants requesting asthma management information to their medical team. Participants will also be informed of the limitations of the role of their assigned coach.

Supervision will occur on a monthly basis with [name] and/or [name]. This training system worked well with prior studies conducted by [name].

D.10. STATISTICAL ANALYSES

General Considerations

All analyses will be conducted on an intention-to-treat paradigm using all data collected. All analyses will be conducted with two-tailed $\alpha=0.05$ for significance.

To address aim 1: To measure completion of the intervention's components by participants randomized to the intervention. Summary statistics of all variables will be described. For continuous variables, we will calculate the mean, median, standard deviation, minimum and maximum. For categorical variables, we calculate the count and the percentage.

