To address aim 2: To determine the effect that the stress management intervention has on the primary measured outcome: symptom free days. Other patient/family-centered outcomes will include parent stress, quality of life, asthma morbidity, healthcare utilization, and medication adherence. Baseline demographic characteristics will first be compared in univariate fashion between the two groups using the chi-squared test for categorical variables and the t-test for continuous variables. If any variable is not balanced by randomization, it will be used as a covariate in all secondary analyses. To test the hypothesis that the time average of number of symptom-free days over a two week period (primary outcome) at 3 and 6 month follow-up will be significantly higher among parents in Arm 2 (intervention) than in Arm 1 (usual care), a two sample t-test will be used to compare difference of mean symptom-free days over a two week period between the two arms with point estimates, 95% CI and p values being reported. Depending on the degree of dispersion, we may need to employ a Poisson or negative binomial model.

In secondary analysis, we will further explore the effect of the intervention by fitting random effect mixed models that (1) adjust for baseline covariates of interest, considered *a priori* or that differ between groups at baseline and are relevant to change in symptom-free days; (2) test for interaction between treatment effects and other covariates; and (3) examine patients who complete intervention and follow-up (per protocol analysis).

For continuous secondary outcomes, we will use the same approach as described above. For the categorical secondary outcomes, we will use the chi square test of whether relative rates between groups differ from 1. All subsequent estimates of relative rates (RR) will be adjusted (at the minimum) for age, sex, race/ethnicity and other covariates using generalized estimating equations (GEE). All estimates of RR will be reported with 95% confidence intervals (CIs). For measures of healthcare

utilization, the analysis will compare adjusted rates and RRs at 3 and 6 follow up. Depending on the degree of dispersion in the rates, these models will be based on either Poisson or negative binomial regression models.

Sensitivity analyses will be conducted to account for missing data. These will estimate the highest and lowest potential treatment effect for primary and secondary outcomes.

Missing Data

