Clinical research staff will be trained in the importance of completing all data fields. Based on our prior studies, we anticipate a rate of missing data for the primary outcome of <5%. All efforts will be made to minimize patient dropout. Frequent data queries will allow us to track missing data and retrain staff as needed. Sensitivity analyses will be conducted as described above. Reasons for participant drop out will be collected and reported. In cases of missing data, we will use multiple imputation (MI) to impute the missing values.

Sample Size Considerations: Power Analysis

This study is designed to detect the smallest clinically significant difference in mean symptom free days (SFD) between the intervention and control groups.

The initial sample size calculation was based on previous data from other studies, the improvements of 0.9-1.0 SFD per 14 days are feasible, the standard deviation of SFD is 2.7, and the within subject correlation is 0.3. Power analysis was calculated for the intervention effect on SFD while justifying two assessments for each subject. The table shows the total sample size needed to detect differences in SFD from 0.9 to 1.0 with different within subject correlation. The sample size of 152 is needed to detect the difference of 1.0 SFD with standard deviation of SFD of 2.7, within subject correlation of 0.3, power of 0.8 at alpha level of 0.05. With anticipation of attrition rate of 10%, we initially planned to enroll 168 children.

The sample size was recalculated on September 14, 2015, based on the baseline data collected from the first 60 participants, which showed the following: mean was 10.25 days, median was 11.5 days, standard deviation was 4.12. The sample distribution is not normal and approximated a Poisson distribution. Based on this distribution, the calculated sample size is 188, as can achieve 80% power at a 0.05 significance level to detect a response rate ratio of 1.15 with baseline response rate 0.8. Therefore, with 10% percent attrition rate, we now plan to enroll 207 participants.

| Power Calculation with Standard Deviation of 2.7, Power of 0.8, Alpha level of 0.5 | | | |
|---|--------------------|------------|-------------------------------|
| Difference | Correlation | N | N (with 10% attrition) |
| 0.9 | 0.1 | 158 | 174 |
| 0.9 | 0.15 | 166 | 183 |
| 0.9 | 0.2 | 172 | 190 |
| 0.9 | 0.25 | 180 | 198 |
| 0.9 | 0.3 | 186 | 205 |
| 0.9 | 0.35 | 194 | 214 |
| 0.9 | 0.4 | 200 | 220 |

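### Shared coaches treat only the intervention arm, and neither the analysis nor the sample size allows for possible correlation of outcomes within coach

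*Protocol*

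**What the plan says.** **Delivery.** Dyads are randomized individually (Protocol D.5). In the intervention arm, "Four sessions as summarized below will be delivered by a trained community wellness coach" (D.3, Component 1). Parents in that arm are also invited to rolling peer support groups, of which D.3 says: "The community wellness coaches will facilitate these sessions". The coaches reinforce the content by calls and texts. D.9 refers to each participant's assigned coach. Under D.5, control families hear from the study team only for follow-up interviews and contact updates, apart from the clinic's own care coordination, which both arms receive.

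**Analysis.** For the primary outcome, D.10 says that "a two sample t-test will be used to compare difference of mean symptom-free days over a two week period between the two arms". A 95% CI and a p value go with it. If the counts prove too dispersed, D.10 allows a switch to Poisson or negative binomial regression. Further models are planned as secondary work: "we will further explore the effect of the intervention by fitting random effect mixed models that (1) adjust for baseline covariates of interest". The random effect is not identified, and neither coach nor peer group is named. The SAP adds intention-to-treat, per-protocol, interaction and dose-response analyses. It lists uptake, satisfaction and fidelity variables, including session location and format, but not coach.

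**Sample size.** The initial calculation in D.10 reads: "The sample size of 152 is needed to detect the difference of 1.0 SFD with standard deviation of SFD of 2.7". It assumes 80% power, a 0.05 level and a correlation of 0.3 between a child's two assessments. The only correlation in that section is between repeated assessments of the same child. The later recalculation to 188 (207 enrolled) mentions no correlation between children.

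**The concern.** This is a partially nested design: children in one arm are grouped by therapist, and those in the other are not. If some coaches obtain better results than others, children who share a coach have correlated outcomes. The mean of the intervention arm then varies more than its independent-observations standard error says.

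A coach effect is plausible here, though not shown. The formative work in Protocol C.4 found that parents valued the relationship with the interventionist. D.9 allows coaches of different backgrounds. The primary outcome is reported by the parent, who is the person coached, and section B says that stress may change how a parent perceives the child's symptoms.

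At stake are the stated precision of the treatment effect and the power to detect it. As written, the plan would neither detect nor report a coach effect. The count models would have the same gap as the t-test.

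**Working it through.** **1. Reproduce the plan's own figure.** Inputs from D.10: difference 1.0 symptom-free day, SD 2.7, within-subject correlation 0.3, two assessments, two-sided alpha 0.05, power 80%.

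- SD of the two-visit average = 2.7 × √((1 + 0.3)/2) = 2.177.
- n per arm = 2 × 2.177² × (1.960 + 0.842)² / 1.0² = 74.4, so 75 per arm and 150 in total.

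The protocol states 152. Agreement within 2 under full independence means that no clustering allowance is built into that figure.

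**2. Inputs for the clustering check.**

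- Analysed per arm: 188/2 = 94. The 188 is in D.10 and the SAP; 1:1 allocation is assumed, because the ratio is not stated.
- Number of coaches k: not stated; 2, 4 and 8 are assumed.
- ICC by coach: not stated; 0 to 0.05 is assumed.
- Equal caseloads, and equal total variance in the two arms: assumed.

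**3. Formulas.**

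- Caseload m = 94/k.
- Design effect in the intervention arm, DE = 1 + (m − 1) × ICC. Controls have a design effect of 1.
- Variance factor for the difference, f = (1 + DE)/2.
- True SE / t-test SE = √f.
- Coverage of the nominal 95% CI = 2Φ(1.96/√f) − 1.
- Power of an analysis that uses the true SE, starting from 80% = Φ(2.80/√f − 1.96).

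**4. Worked case: 4 coaches, ICC 0.02.** m = 23.5; DE = 1 + 22.5 × 0.02 = 1.45; f = 1.225; √f = 1.107. Coverage is 92.3%. Power = Φ(2.80/1.107 − 1.96) = 72%.

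**5. Range.**

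| Coaches | ICC | SE ratio | CI coverage | Power |
|---|---|---|---|---|
| any | 0 | 1.00 | 95.0% | 80% |
| 2 | 0.01 | 1.11 | 92.3% | 71% |
| 2 | 0.02 | 1.21 | 89.5% | 64% |
| 2 | 0.05 | 1.47 | 81.9% | 48% |
| 4 | 0.01 | 1.05 | 93.7% | 76% |
| 4 | 0.02 | 1.11 | 92.3% | 72% |
| 4 | 0.05 | 1.25 | 88.3% | 61% |
| 8 | 0.01 | 1.03 | 94.4% | 78% |
| 8 | 0.02 | 1.05 | 93.7% | 76% |
| 8 | 0.05 | 1.13 | 91.8% | 70% |

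Simulation of the ordinary t-test interval (20,000 runs per setting, coaches drawn at random in each run) agrees. With 4 coaches, coverage was 95.2, 93.8, 92.5 and 88.2% at an ICC of 0, 0.01, 0.02 and 0.05.

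The power column uses normal quantiles. The small-sample degrees of freedom that a coach-level analysis needs would lower it further, most of all with 2 coaches. The SE ratio does not depend on the effect size or the outcome SD.

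**The case against.** The strongest case against is that nothing in the documents shows a positive ICC. Coaches work with parents, while the outcome is the child's symptom days, so any coach effect is indirect. The SAP's per-protocol definition foresees that some families will not complete the sessions, and under intention to treat non-attendance dilutes any coach correlation. All of this stands. It is why the range above starts at zero.

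Four stronger readings are tempting, and the documents do not support them.

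- **That the interval is too narrow as a matter of fact.** This needs a positive ICC and an intended inference to coaches in general. For the effect as delivered by the coaches actually employed, the t-test holds its level. Simulated with fixed coach effects averaging zero (2, 4 or 8 coaches; coach variance 1% or 5%), type I error was 4.5–5.0% with equal caseloads and 4.9–5.3% with random coach assignment. Neither document says which inference is meant.
- **That the 5% error rate is lost.** If the intervention does nothing, coaches induce no correlation and individual randomization protects the test. Inflation (11.7% with 4 coaches and ICC 0.05) needs coaches whose effects differ yet average zero, and who are regarded as a random sample. Coverage and power are the relevant harms.
- **That the peer groups are a second layer of clusters.** They are by invitation and rolling, so they have no fixed membership. Coach is the usable unit.
- **That coach identity is already in the data.** D.6 describes uptake and fidelity only as staff data collection, and the SAP's list does not include coach.

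It is also fair to object that with 2 to 4 coaches the variance component rests on about 1 to 3 degrees of freedom. That argues against making the coach model primary. It does not argue for leaving coach out of the plan.

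**Conclusion.** The gap is real and its consequence is conditional. The design is partially nested, and neither document allows for that in the primary test, its count-model alternative or the sample size. Whether the reported interval will be too narrow depends on two things the documents do not settle: whether outcomes correlate within coach, and whether the conclusion is meant to reach beyond the coaches employed. If both hold, with 94 per arm and 4 coaches, the true SE exceeds the t-test SE by 5, 11 or 25% at an ICC of 0.01, 0.02 or 0.05. Put the other way, the t-test SE is about 5, 10 or 20% too small. Fewer coaches make this worse and more coaches make it milder. This is a worthwhile, inexpensive improvement to the SAP; it is not a demonstrated error in the trial's inference.

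**What to change.** 1. Record the assigned coach for every intervention participant. Use the assigned coach, not the coach who delivered sessions, so that families who attend nothing stay in the intention-to-treat analysis.
2. Keep the planned primary test.
3. Prespecify in the SAP, before any analysis by arm, a partially nested analysis of the primary contrast: a random coach effect in the intervention arm only, controls as singletons, and Satterthwaite or Kenward-Roger degrees of freedom. If a count model replaces the t-test, put the same coach term in that model.
4. Report it beside the primary result, with the estimated ICC and the number of coaches.
5. If there are too few coaches to estimate the variance (2, for example), say in the SAP and the report that the inference is limited to the coaches employed. The nested model comes close to its nominal level with 4 or more coaches, but not with 2.

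The cost is one data field, a paragraph in the SAP and one more model, with no added participants, visits or instruments. The downside is a second, wider interval with few degrees of freedom.

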This study is a single blind, prospective randomized controlled trial comparing the IMPACT DC Asthma Clinic intervention of guideline-based clinical care, education, and short-term care coordination (usual care) to usual care plus parental stress management in a cohort of up to 250 parent-child dyads.

This study will employ a parallel-groups RCT design. Outcomes data will be collected by interviews at enrollment (baseline), 3 months post-enrollment, 6 months post-enrollment, and 12 months post-enrollment. The 12 month follow-up data will be collected only for a subset of participants.

D.2. Usual Care

All participants in both the usual care and intervention arms of the study will receive guideline-based asthma care in the IMPACT DC Asthma Clinic, supplemented by three months of limited care coordination services to address barriers to care.

The IMPACT DC Asthma Clinic is a fully validated and bilingual clinical intervention³³ that has operated at Children's National since 2004. It focuses on at-risk youth with an over-dependence on EDs for episodic care. It provides care to approximately 1000 new patients per year, and has won multiple national and local awards, including the EPA's 2006 National Environmental Leadership Award in Asthma Management, the 2012 DC Chartered Healthcare "*Making a Difference*" Health Disparities Award, and the 2012 DC Hospital Association *Haynes Rice Community Service Award*.

IMPACT DC's conceptual model begins with the premise that effective longitudinal asthma care is a broad continuum involving the child surrounded by his/her family, primary medical care home, hospital, ED, community pharmacist, insurance case manager, and school nurse. The vision continues with the novel idea that the ED can and should be a critical and proactive part of this continuum, particularly for children who use the ED frequently and/or are poorly connected with their medical homes. The IMPACT DC Asthma Clinic therefore targets children who are heavily dependent on EDs for episodic care. It provides a comprehensive source of asthma education, medical care, and care coordination designed to transition patients to more effective longitudinal asthma care in their primary medical care homes. Patients are referred for consultative care from EDs, inpatient units, primary clinicians, and school nurses.

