Obstacle 2: Refusals. Families vary in their willingness to participate in research. Solutions include:

- Train research staff to appropriately present studies to families and to partner with investigators to respond to questions.
- Engage the Research Subject Advocate to empower families to make informed choices regarding research participation.

Informed Consent: Written consent will be obtained from interested study participants prior to the initiation of study activities. A single document will be used to document consent for the parents' own participation, as well as their permission for their child's participation. In addition, children age 7 and older will provide assent in accordance with Children's National's policy. The Informed Consent form that will be approved by the Children's National Health System IRB, and will supplement but not replace the dialogue between participants and research personnel. Additional requirements include:

- The Consent Form will be prepared at approximately an 8th grade reading level, with appropriate lay descriptions of technical terms wherever used.
- Participants will be allowed ample time to review the document and ask staff questions prior to deciding whether or not to participate.
- Copies of the Consent Form will be given to participants for their records.

After obtaining informed consent, study staff will administer a baseline questionnaire as described in Section D.6. Outcomes. The baseline questionnaire will be completed within ten days of consent.

Randomization: After completion of the baseline measure, the participant will be randomized to one of the study's two arms using RedCap.

Participants randomized to the intervention arm will then be provided with an orientation to the intervention, and instructed on when they will be contacted by the intervention team. These participants will also receive short-term care coordination by the IMPACT DC Asthma Clinic team

according to the Clinic’s standard protocol, and will receive periodic requests for updated contact information.

Participants randomized to the control arm will receive short-term care coordination by the IMPACT DC Asthma Clinic team according to the Clinic’s standard protocol, but will not receive any additional contact by the study team until the follow-up phone interviews with the exception of periodic requests for updated contact information.

D.6. Outcomes

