Other asthma outcomes were selected for their importance to both parents/patients and decision makers. Asthma morbidity, control, and exacerbations are of primary importance to parents, while clinicians and other decision-makers also focus on medication adherence, healthcare utilization, and exacerbations.

In addition, this study includes psychosocial outcomes of key importance to both parents and decision makers. Parents indicated a particular interest in the psychological well-being of their children, and clinicians and service providers have indicated interest in parental well-being, as this impacts a wide range of child-centered outcomes.

Analysis of the following variables is planned:

| Outcome | Measure |
|----------------------------------|--|
| Primary Outcome | |
| Symptom-free days | Days with no symptoms of asthma in prior 14d |
| Secondary Outcomes | |
| Asthma morbidity | Daytime and nighttime symptoms in prior 14d, missed school in prior 14d |
| Asthma severity | Asthma symptoms in prior 1m, and oral steroid use in prior year |
| Asthma control | Asthma symptoms in prior 1m, and oral steroid use in prior year |
| Asthma medications and adherence | Use of medications in prior 2d, and beliefs regarding asthma medications |
| Healthcare utilization | Utilization in 12m prior to enrollment and during follow-up period, including emergency department visits, hospital and ICU admissions, primary care visits, and urgent care visits. |
| Exacerbations | Courses of systemic steroids |
| Family stress | Stressful events in prior 30d |
| Parental stress | Perceived Stress Scale (PSS) |
| Parental depression | Center for Epidemiologic Studies Depression |

| | |
|------------------------------------|--|
| | Scale (CES-D) |
| Child anxiety | PROMIS Parent Proxy Anxiety |
| Child depression | PROMIS Parent Proxy Depressive Symptoms |
| Quality of life | Pediatric Asthma Caregiver Quality of Life Questionnaire (PACQLQ) |
| Caregiver smoking behavior | Cigarettes smoked per day |
| Coping strategies | Brief COPE |
| Mindfulness | Interpersonal Mindfulness in Parenting |
| Resilience | Revised Life Orientation Test (LOT-R) |
| Covariates | |
| Sociodemographics | Race, ethnicity, family history, parent education attainment, household income |
| Home exposures | Exposure to environmental tobacco smoke |
| Health literacy | Single Item Literacy Screener (SILS) |

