Baseline Sociodemographic factors	Age, gender, race, ethnicity, insurance type, parent education, household income, family medical history, parent health literacy, parental resilience
Intervention uptake, satisfaction, and fidelity	Completion of 1:1 session, completion of group sessions, location/format of sessions, use of stress management techniques, use of techniques with children
Asthma severity	
 • NAEPP classification, as determined by IMPACT DC clinician
Asthma control	
 • NAEPP classification, as determined by IMPACT DC clinician • ACT score

Table of Planned Analyses

Breathe with Ease: A Unique Approach to Managing Stress (BEAMS)

PI: [name], MPH

Final 11.25.16

We will examine interactions between primary and secondary outcomes and

- baseline asthma variables (severity/control, health care utilization, exacerbations),
- baseline psychosocial variables (parental stress and depression, resilience, child anxiety and depression, quality of life)
- baseline demographic factors

In addition, we will examine interactions between primary and secondary outcomes and intervention uptake within the intervention group.

Key planned analyses include:

- Interaction between primary outcome and parental age, education, household income, child age and gender
- Interaction between primary outcome and baseline child asthma severity, control, and history of unscheduled healthcare utilization
- Interaction between primary outcome and baseline parental depression
- Interaction between primary outcome and baseline parental stress
- Interaction between primary outcome and baseline parental resilience
- Interaction between primary outcome and baseline child depression
- Interaction between primary outcome and baseline child anxiety
- Interaction between primary outcome and baseline asthma severity/control
- Dose-response analysis of intervention uptake (session completion and parent report of technique utilization)

Sample Size Calculation: The sample size was recalculated on September 14, 2015 based on the baseline data collected from the first 60 participants, which showed the following:

- mean = 10.25 days
- standard deviation = 4.12
- median = 11.5 days.

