The sample distribution is not normal and approximated a Poisson distribution. Based on this distribution, the calculated sample size is 188 to achieve 80% power at a 0.05 significance level to detect a response rate ratio of 1.15 with baseline response rate of 10.25. Therefore, with 10% percent attrition rate, we planned to enroll 207 participants.

The primary analyses for this study will be conducted at 6m FU, and the same analyses will be completed with the 12m FU data.

The primary analysis for this study will be by intention to treat.

A per-protocol analysis will also be conducted. Per protocol will be defined as completion of all four one-on-one sessions.

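### Half to three quarters of the steroid look-back in follow-up asthma severity and control predates randomisation, and the SAP reclassifies both as control variables, so it specifies no follow-up comparison of control

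*Protocol*

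**What the plan says.** **Protocol.** The table of planned variables in D.6 places asthma severity and asthma control among the secondary outcomes. Both rows carry the same measure: "Asthma symptoms in prior 1m, and oral steroid use in prior year". D.6 also states: "Asthma morbidity, control, and exacerbations are of primary importance to parents". Interviews follow enrolment at these times (D.1): "3 months post-enrollment, 6 months post-enrollment, and 12 months post-enrollment". D.1 adds: "The 12 month follow-up data will be collected only for a subset of participants". On allocation, D.5 says: "After completion of the baseline measure, the participant will be randomized to one of the study's two arms using RedCap". The timeline in D.10 puts enrolment, baseline interview and randomisation all at month 0. D.10 gives a generic analysis for continuous and categorical secondary outcomes. The healthcare utilisation row in D.6 covers ED visits, hospital and ICU admissions, and "primary care visits, and urgent care visits".

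**SAP.** In the Table of Planned Analyses, neither severity nor control appears among the secondary or exploratory outcomes. Both sit under Control Variables, measured as "NAEPP classification, as determined by IMPACT DC clinician"; the control row adds the ACT score, with no time point. The interaction list uses baseline severity and control as effect modifiers. The utilisation row has ED visits, hospital admissions, ICU admissions and primary care visits, and no urgent care. On timing: "The primary analyses for this study will be conducted at 6m FU", with the same analyses repeated on the 12-month data.

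**The concern.** Two problems meet on one variable.

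First, a one-year look-back taken 3 or 6 months after randomisation mixes steroid use that the intervention could have changed with steroid use that it could not. Nothing in D.6 adapts the window for these two rows. Elsewhere the plan does keep the periods apart: the utilisation row in D.6 and the exacerbation row in the SAP each distinguish the time before enrolment from follow-up.

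Second, the documents disagree on whether control is an outcome at all and on how it is measured. Under the Protocol it is a parent- or record-derived secondary outcome; under the SAP it is a clinician's class plus an ACT score, used as a control variable. Until this is settled, the choice of whether to compare control between arms, and with which measure, could be made after data have been seen. That matters for an outcome the Protocol itself ranks so highly for parents.

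The missing urgent care visits are a smaller matter of the same kind: the Protocol plans to analyse them, and the SAP list would compare unscheduled care incompletely.

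**Working it through.** The plan states no figure for this point, so there is nothing to reproduce. The check has three parts.

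**1. Share of the steroid window before randomisation.** Inputs: 12-month look-back (D.6), interviews at t = 3, 6 and 12 months (D.1), randomisation at month 0 (D.5 and the D.10 timeline). Share = (12 − t)/12.

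- Month 3: 9/12 = 75%
- Month 6: 6/12 = 50%
- Month 12: 0/12 = 0%

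The 1-month symptom component lies wholly after randomisation at every follow-up.

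**2. Effect on the steroid component.** Assumptions, since the documents give no steroid-course rates: Poisson counts; true post-randomisation rate ratio r between 0.5 and 0.8; usual-care rate after randomisation equal to c times the rate before, with c = 1 as the main case.

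Apparent rate ratio = [(12 − t) + t·c·r] / [(12 − t) + t·c].

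The pre-randomisation months have the same expectation in both arms, so the absolute difference in expected courses is the same whether or not they are counted. Only the variance rises. The ratio of sample sizes (one-year window against counting since randomisation) is therefore the ratio of the summed Poisson variances:

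[2(12 − t) + t·c·(1 + r)] / [t·c·(1 + r)].

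With c = 1:

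| Visit | r | Apparent rate ratio | Share of true log effect kept | Sample size ratio |
|---|---|---|---|---|
| Month 3 | 0.5 | (9 + 1.5)/12 = 0.875 | ln 0.875 / ln 0.5 = 19% | (18 + 4.5)/4.5 = 5.0 |
| Month 3 | 0.8 | (9 + 2.4)/12 = 0.95 | ln 0.95 / ln 0.8 = 23% | (18 + 5.4)/5.4 = 4.3 |
| Month 6 | 0.5 | (6 + 3)/12 = 0.75 | ln 0.75 / ln 0.5 = 42% | (12 + 9)/9 = 2.3 |
| Month 6 | 0.8 | (6 + 4.8)/12 = 0.90 | ln 0.90 / ln 0.8 = 47% | (12 + 10.8)/10.8 = 2.1 |

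At month 12 the window is clean and all ratios are 1.

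Sensitivity: clinic care may itself lower the rate in both arms. Taking c = 0.54 purely for illustration (it is the ED-visit rate ratio for the clinic programme in Protocol C.1, not a steroid figure), the sample size ratio becomes (18 + 2.43)/2.43 = 8.4 to (18 + 2.916)/2.916 = 7.2 at month 3, and (12 + 4.86)/4.86 = 3.5 to (12 + 5.832)/5.832 = 3.1 at month 6.

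**3. The two documents side by side.**

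| Item | Protocol D.6 | SAP table |
|---|---|---|
| Role of severity and control | Secondary outcomes | Control variables |
| Measure | 1-month symptoms plus prior-year oral steroids | Clinician NAEPP class; ACT score added for control |
| Follow-up comparison between arms | Generic secondary-outcome analysis (D.10) | None specified |
| Urgent care visits | Included | Absent |

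The only clinic visit on the D.10 timeline is at month 0, and follow-up interviews are by phone (D.6). No scheduled visit would supply a clinician-assigned class after baseline, so the SAP's main measure of control could not serve as a follow-up outcome as it stands.

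**The case against.** The strongest reply is that the two problems cannot bite together. If the Protocol governs, control is still a secondary outcome with an analysis. If the SAP governs, severity and control are no longer outcomes, so the long look-back dilutes no planned comparison, and a prior-year window is harmless in a baseline covariate. This stands as logic, but it shows why the documents must be reconciled: each route leaves a different gap.

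Four stronger readings are tempting and are not supported.

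- *Most of the window is pre-randomisation.* A reader might carry the month 3 figure over to the whole trial. It is exactly half at month 6, the SAP's primary analysis time, and nil at month 12.
- *Control has no usable follow-up analysis.* D.10 still covers it, its symptom component is wholly post-randomisation, and the SAP keeps close relatives: 14-day morbidity (symptoms, activity limitation, quick-relief use) and steroid courses split at enrolment. These do not replace control, but much of its content is still compared.
- *The SAP would adjust the effect away with follow-up severity or control.* The heading alone does not settle timing, since the same block holds intervention uptake, which arises after randomisation. But the SAP's interaction list repeatedly says baseline, D.10 speaks of baseline covariates, and no later clinician class is scheduled. Only the ACT score has no stated time. This is a loose end, not a stated plan.
- *At month 6 four times as many dyads are needed.* Halving the effect suggests 1/0.5² = 4, but that compares with twelve post-randomisation months, which do not exist at month 6. Against counting since randomisation, Poisson counts at a constant rate give 2.1 to 2.3.

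On urgent care, a reader might infer that visits moving from the ED to urgent care would look like benefit. No document suggests that the intervention does this. The omission from the SAP list is real; the consequence is conjecture.

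**Conclusion.** The point holds in a limited form. At months 3 and 6, 75% and 50% of the steroid look-back for severity and control precedes randomisation. This costs precision and shrinks the relative effect on that component; because the earlier months are balanced in expectation, it does not bias the test under the null. The sample size penalty is about 4.3 to 5 times at month 3 and 2.1 to 2.3 times at month 6. It rests on Poisson counts, a constant usual-care rate and an assumed true rate ratio of 0.5 to 0.8, and would be larger if usual care also lowers the rate. It applies to the steroid component only: D.6 gives no rule for combining it with symptoms, so the effect on the full severity or control measure cannot be computed.

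Separately, Protocol and SAP conflict on the role and the measure of severity and control, and the SAP specifies no between-arm follow-up comparison of control. The SAP utilisation list is also incomplete against the Protocol. The primary outcome is untouched. These are secondary-outcome defects that cost little to put right.

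**What to change.** 1. In Protocol D.6, for months 3 and 6, count oral steroid courses only since randomisation. Alternatively, score control on the 1-month symptom items alone, or on the ACT score if it is collected at follow-up.
2. Reconcile the documents: list follow-up asthma control as a secondary outcome in the SAP, with its measure and visits, and state that only baseline severity, control and ACT values serve as control variables.
3. Restore urgent care visits to the SAP utilisation row.

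The cost is wording in the two documents. The Protocol already plans the symptom, steroid and urgent care data; whether the ACT is collected at follow-up is not stated and needs confirming before it is chosen. The downsides are fewer steroid events in a shorter window and one more secondary outcome to report.
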